 - Man who agrees to take appropriate precautions to avoid fathering children (with at least 99% certainty) from screening through safety follow-up. Permitted methods that are at least 99% effective in preventing pregnancy should be communicated to the subject and their understanding confirmed.
- Written informed consent and/or assent from the subject, parent, or guardian.
- Willingness to comply with all study visits and procedures.

Key Exclusion Criteria:

- Has received more than 1 allo-HSCT.
- Has received more than 1 systemic treatment in addition to corticosteroids for acute GVHD.
- Presence of GVHD overlap syndrome as per NIH guidelines.
- Presence of an active uncontrolled infection. An active uncontrolled infection is defined as hemodynamic instability attributable to sepsis or new symptoms, worsening physical signs, or radiographic findings attributable to infection. Persisting fever without signs or symptoms will not be interpreted as an active uncontrolled infection.
- Known human immunodeficiency virus infection.
- Active hepatitis B virus (HBV) or hepatitis C virus infection that requires treatment or at risk for HBV reactivation. At risk for HBV reactivation is defined as hepatitis B surface antigen positive or anti-hepatitis B core antibody positive. Previous test results obtained as part of standard of care before allo-HSCT that confirm a subject is immune and not at risk for reactivation (ie, hepatitis B surface antigen negative, surface antibody positive) may be used for purposes of eligibility and tests do not need to be repeated. Subjects with previous positive serology results must have negative polymerase chain

reaction results. Subjects whose immune status is unknown or uncertain must have results confirming immune status before enrollment.

- Serum creatinine > 2.0 mg/dL or creatinine clearance < 40 mL/min measured or calculated by Cockroft-Gault equation.
- Subjects with evidence of relapsed primary disease, or subjects who have been treated for relapse after the allo-HSCT was performed.
- Unresolved toxicity or complications (other than acute GVHD) due to previous allo-HSCT.
- Any corticosteroid therapy for indications other than GVHD at doses of methylprednisolone or equivalent > 1 mg/kg per day within 7 days of enrollment.
- Severe organ dysfunction unrelated to underlying GVHD, including:

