Dacliz + infliximab	Retro	22	Day 42 ^b	0.45	0.82	0.86
Dacliz/inflix/horse ATG	Retro	12	Best ^b	1.00	1.00	0.73
Sirolimus	Retro	34	Best	0.44	0.76	0.48

Figure 2: Summary of Studies Evaluating Agents for Second-Line Therapy of Acute GVHD^a

aGVHD = acute graft-versus-host disease; ATG = antithymocyte globulin; CR = complete response; ECP = extracorporeal photopheresis; MMF = mycophenolate mofetil; PR = partial response; Retro = retrospective.

^a Treatment results that fall outside the 95% confidence interval (CI) for the aggregated overall average of all studies are shown in bold.

^b The report did not indicate whether absence of further systemic treatment was a criterion for response. In all other reports, subjects who had further systemic treatment were classified as not having a CR or PR.

Source: Martin et al 2012.

Given these data, the choice of a second-line regimen is made based on the outcome of prior treatments, desired toxicity profile, considerations for drug interactions, logistical practicality, costs, and subject and physician preferences. Second-line treatments, especially those associated with suppression of T cells, are associated with increased infection and viral reactivation (including cytomegalovirus [CMV], Epstein-Barr virus, human herpes virus 6, adenovirus, and polyoma).

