3.2. Subject Exclusion Criteria

- 1. Has received more than 1 allo-HSCT.
- 2. Has received more than 1 systemic treatment in addition to corticosteroids for acute GVHD.
- 3. Presence of GVHD overlap syndrome as per NIH guidelines (Jagasia et al 2015).
- 4. Subjects who have had a splenectomy.
- 5. Presence of an active uncontrolled infection. An active uncontrolled infection is defined as hemodynamic instability attributable to sepsis or new symptoms, worsening physical signs, or radiographic findings attributable to infection. Persisting fever without signs or symptoms will not be interpreted as an active uncontrolled infection.
- 6. Known human immunodeficiency virus infection.

- 7. Active hepatitis B virus (HBV) or hepatitis C virus (HCV) infection that requires treatment or at risk for HBV reactivation. At risk for HBV reactivation is defined as hepatitis B surface antigen positive or anti-hepatitis B core antibody positive. Previous test results obtained as part of standard of care before allo-HSCT that confirm a subject is immune and not at risk for reactivation (ie, hepatitis B surface antigen negative, surface antibody positive) may be used for purposes of eligibility, and tests do not need to be repeated. Subjects with previous positive serology results must have negative polymerase chain reaction results. Subjects whose immune status is unknown or uncertain must have results confirming immune status before enrollment.
- 8. Serum creatinine > 2.0 mg/dL or creatinine clearance < 40 mL/min as measured or calculated by Cockroft-Gault equation.
- 9. Subjects with evidence of relapsed primary disease, or subjects who have been treated for relapse after the allo-HSCT was performed.
- 10. Unresolved toxicity or complications (other than acute GVHD) due to previous allo-HSCT.
- 11. Any corticosteroid therapy for indications other than GVHD at doses of methylprednisolone or equivalent > 1 mg/kg per day within 7 days of enrollment.
- 12. Severe organ dysfunction unrelated to underlying GVHD, including:
 - a. Cholestatic disorders or unresolved veno-occlusive disease of the liver (defined as persistent bilirubin abnormalities not attributable to GVHD and ongoing organ dysfunction).

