Hepatitis screening	7.5.6.4	Х		•													
Serum pregnancy test (childbearing females only)	7.5.6.3	х										х					
Urine pregnancy test ^e (childbearing females only)	7.5.6.3			х													
PK assessment ^f	7.7		х		Х	Х											
Correlative study blood collection	7.8	х	x		х	х		х				\mathbf{X}^{g}	х	х	х	х	

^a A ± 2-day window is permitted to facilitate scheduling during the treatment phase.
 ^b Day 1 laboratory assessments do not need to be repeated if screening assessments were performed in preceding 7 days.
 ^c After Day 56, visits will occur every 28 days and will include all Day 56 assessments.

^d The Day 365 visit will also serve as the regularly scheduled visit occurring every 28 days after Day 56 (ie, Day 364).

* Urine pregnancy tests are only required if medically indicated and should be confirmed with a serum pregnancy test.

^f Samples to be collected at predose and at 1 hour \pm 15 minutes, at 2 hours \pm 30 minutes, and between 4 and 8 hours postdose. ^g Day 56 only.

Serum Chemistries	Hematology ^a	Other
Albumin	Hematocrit	Serum pregnancy test
ALP	Hemoglobin	Urine pregnancy test ^b
ALT	Mean corpuscular volume	
AST	Platelet count	
Bicarbonate	Red blood cell count	
Blood urea nitrogen	Reticulocyte count	
Calcium	White blood cell count	
Chloride	White blood cell differential (5 parts):	Hepatitis Screening Tests
Creatinine	Basophils	
Glucose	• Eosinophils	Hepatitis B surface antigen
Lactate dehydrogenase	• Lymphocytes	Hepatitis B surface antigen antibody
Phosphorus	Monocytes	Hepatitis B core antibody
Potassium	Neutrophils	Hepatitis C virus antibody
Sodium	·······	HCV-RNA
Total bilirubin		HEV-KNA HBV-DNA
Total protein		

 Table 7:
 Clinical Laboratory Analytes

ALP = alkaline phosphatase.

^a Hematology and chemistry assessments will be performed locally.

^b Urine pregnancy tests are only required if medically indicated.

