7.5.6.4. Hepatitis Screening

Subjects with active HBV or HCV infection that requires treatment or who are at risk for HBV reactivation are excluded from the study. At risk for HBV reactivation is defined as hepatitis B surface antigen positive or anti-hepatitis B core antibody positive. Prior test results obtained as part of standard of care before allo-HSCT confirming that a subject is immune and not at risk for reactivation (ie, hepatitis B surface antigen negative, surface antibody positive) may be used for purposes of eligibility, and tests do not need to be repeated. Subjects with prior positive serology results must have negative polymerase chain reaction results. Subjects whose immune status is unknown or uncertain must have results confirming immune status before enrollment as per Table 7.

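### The hepatitis B test waiver defines immune status without core antibody, so a site can accept a subject whose core antibody was never measured, although core-antibody positivity is an exclusion

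*Protocol*

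**What the plan says.** Protocol 3.2, criterion 7, excludes subjects with active hepatitis B or C that needs treatment and subjects at risk of HBV reactivation. Risk is given an explicit definition: "At risk for HBV reactivation is defined as hepatitis B surface antigen positive or anti-hepatitis B core antibody positive". Either marker is enough.

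The next sentence is a waiver. It accepts standard-of-care results from before the transplant, and the tests need not be done again, where those results show the status described here: "immune and not at risk for reactivation (ie, hepatitis B surface antigen negative, surface antibody positive) may be used for purposes of eligibility". Two further sentences follow. One reads "Subjects with previous positive serology results must have negative polymerase chain reaction results". The other requires results confirming immune status before enrollment where that status is unknown or uncertain.

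The synopsis carries the same waiver: "ie, hepatitis B surface antigen negative, surface antibody positive) may be used for purposes of eligibility and tests do not need to be repeated". Section 7.5.6.4 carries it too, in the sentence that begins "Prior test results obtained as part of standard of care before allo-HSCT confirming that a subject is immune and not at risk for reactivation". That section also ties the last clause to a test panel: "Subjects whose immune status is unknown or uncertain must have results confirming immune status before enrollment as per Table 7". Table 7 lists three HBV serology tests, among them "Hepatitis B core antibody", and also HBV-DNA and HCV-RNA. Table 6 schedules hepatitis tests at screening only.

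**The concern.** The definition of risk and the waiver from testing do not use the same markers. The definition needs surface antigen and core antibody. The waiver describes a subject who is not at risk by surface antigen and surface antibody. A subject can meet the waiver's stated pattern while half of the exclusion remains untested.

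What is at stake is the safety of that subject. If core antibody is in fact positive, someone whom the protocol defines as at risk starts ruxolitinib with methylprednisolone 2.0 mg/kg per day or the prednisone equivalent. Protocol 1.1.2 recognises the general hazard: "Second-line treatments, especially those associated with suppression of T cells, are associated with increased infection and viral reactivation". (The viruses it goes on to list do not include HBV.) Section 3 permits no eligibility deviations and gives subject safety as one reason, so a criterion that about 40 sites will apply should have one meaning.

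**Working it through.** No arithmetic applies beyond counting. The check sets the three statements side by side.

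| Marker | Definition of at risk (3.2) | Waiver parenthesis (synopsis, 3.2, 7.5.6.4) | Table 7 serology |
|---|---|---|---|
| Surface antigen | positive means at risk | must be negative | listed |
| Core antibody | positive means at risk | not mentioned | listed |
| Surface antibody | not mentioned | must be positive | listed |

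The waiver therefore leaves unaddressed 1 of the 2 markers that define risk, and 1 of the 3 HBV serology tests in Table 7. It is the same marker each time, and it is missing in 3 of 3 places. These are counts of wording, not of patients.

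Now take a subject whose pre-transplant record shows surface antigen negative and surface antibody positive, and vary core antibody.

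1. **Core antibody negative on file.** Not at risk under the definition, and the waiver pattern is met. There is no conflict.
2. **Core antibody positive on file.** At risk under the definition. The waiver does not help, because the results on file do not confirm absence of risk.
3. **Core antibody never measured.** The waiver pattern is met as written. The core-antibody half of the definition has not been checked. If the true status is positive, the exclusion applies but nobody knows it.

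Only case 3 is a gap. Three provisions might close it.

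- **The PCR sentence.** It is triggered by an earlier positive serology result. A core antibody that was never measured cannot trigger it. Whether a positive surface antibody counts as positive serology is not stated.
- **The clause on unknown or uncertain status.** In 7.5.6.4 this leads to the Table 7 panel, which would supply the core-antibody result. But a site that follows the parenthesis has already classed the subject as immune, so it has no clear reason to apply the clause.
- **Later testing.** Hepatitis tests are not scheduled after screening. Scheduled chemistry includes ALT, AST and bilirubin, so a liver signal could be seen, but only once it has occurred.

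None of the three reliably catches case 3.

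**The case against.** The strongest reply is that the stricter reading is the natural one. The waiver covers only results that confirm a subject is not at risk, and the sentence immediately before defines risk to include core antibody. A record without core antibody does not confirm absence of risk in that sense. Waiving repetition presupposes a test that was done once. Hepatitis screening is the default in Table 6, so the waiver is an exception and should be read narrowly.

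This has force: a careful site could reach that reading, and the gap cannot be called certain. It does not settle the matter, because the parenthesis opens with ie, which defines, and what it defines is the whole phrase about being immune and not at risk. Where the protocol means an example it writes eg, as in inclusion criterion 5 on engraftment. Two reasonable readings remain.

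Other layers limit the consequence. Criterion 16 excludes conditions that the investigator judges a significant risk, anti-infective prophylaxis may continue under institutional guidelines (5.2.2.4), chemistry is scheduled weekly to Day 56, and Table 2 gives actions for abnormal liver tests. All of this stands, but none of it replaces a core-antibody result before the first dose.

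A reader might also infer that the PCR sentence should be rewritten so that a negative HBV-DNA result never overrides the core-antibody exclusion. The documents do not support going that far. They leave open whether a subject with positive serology and negative PCR may enter, and that is the sponsor's decision. Under such a rule, an HBV-DNA result required of subjects positive for surface antigen or core antibody could never change eligibility, because both groups would already be excluded.

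**Conclusion.** The point holds in a limited form. The waiver's stated pattern can be met with core antibody never measured, and the remaining text does not reliably require the test. That is an inconsistency between a rule and the exclusion it serves, and it should be corrected. Confidence is moderate, because the point turns on how a site reads one sentence.

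The size is one missing marker in one sentence that appears three times. The number of subjects affected is unknown. It would need a record that holds both surface markers but no core antibody, in a subject who is in fact core-antibody positive. The documents give no frequency for either, and none is assumed here.

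Two stronger conclusions might be drawn and are not supported. The first is that the waiver admits subjects already known to be core-antibody positive. It does not: such results cannot confirm absence of risk under the protocol's own definition. Whether the PCR sentence offers them a separate route is a different question, which the text leaves open. The second is that trial results are affected. Nothing in the documents links this wording to the Day 28 response rate, the sample size of about 70 or the threshold of 37 responders.

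**What to change.** Make the same two changes in the synopsis, 3.2 (criterion 7) and 7.5.6.4:

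1. Expand the parenthesis to three markers: surface antigen negative, core antibody negative, surface antibody positive.
2. Add a sentence stating that, if no core-antibody result is on file, the core-antibody test in Table 7 is required at screening.

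Leave the PCR sentence as it is.

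The cost is a short amendment in three places and one blood test, already in the screening panel, for subjects without a result. Subjects with a complete pre-transplant record need nothing more.

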4. INVESTIGATIONAL PLAN

4.1. Overall Study Design

This is an open-label, single-cohort, multicenter Phase 2 study of ruxolitinib in combination with corticosteroids for the treatment of steroid-refractory Grades II to IV acute GVHD. Eligible subjects will begin treatment at ruxolitinib 5 mg BID; if hematologic parameters are stable and no treatment-related toxicity is observed after the first 3 days of treatment, the dose may be increased to 10 mg BID. Ruxolitinib may be tapered after Day 180 provided the subject has achieved a CR or VGPR and corticosteroids have been discontinued for at least 8 weeks. Subjects who are still receiving calcineurin inhibitors or other agents for GVHD prophylaxis at this time may continue to do so at the treating investigator's discretion. Corticosteroids will be administered at a starting dose of 2.0 mg/kg per day (unless otherwise indicated) on Day 1 and will be tapered as appropriate. Subjects will receive study treatment until treatment failure (progression of GVHD, no response, or requiring additional systemic therapy), unacceptable toxicity, or death. Continued use of anti-infective medications, GVHD prophylaxis medications (including calcineurin inhibitors), transfusion support, and topical steroid therapy is permitted.

Severity of GVHD will be assessed from screening through end of treatment (EOT) using the Mount Sinai Acute GVHD International Consortium (MAGIC) guidelines. Adverse events and SAEs will be assessed from the time of consent through 30 to 35 days after the EOT as per National Cancer Institute (NCI) CTCAE v4.03. Subjects will be assessed for efficacy (including overall response, NRM, FFS, DOR, relapse rate, relapse-related mortality rates, and OS), safety (including AEs, SAEs, and clinical/laboratory assessments),

4.2. Measures Taken to Avoid Bias

Acute GVHD response and AEs will be assessed using standardized objective criteria (MAGIC guidelines [Appendix B] and NCI CTCAE v4.03 [2009], respectively).

4.3. Number of Subjects

4.3.1. Planned Number of Subjects

This study will enroll approximately 70 subjects with steroid-refractory acute GVHD from approximately 40 study sites.

4.3.2. Replacement of Subjects

Not applicable.

4.4. Duration of Treatment and Subject Participation

After signing the informed consent form (ICF), screening assessments may be completed over a period of up to 28 days. Each subject enrolled in the study may continue to receive study treatment for as long as benefit is observed and/or treatment withdrawal criteria are not met. If

the subject discontinues study treatment (ie, ruxolitinib and corticosteroids), then the treatment period will end, and the subject will enter the follow-up period (see Section 6.4). The safety follow-up period will last 30 to 35 days, and the survival follow-up period will last until death, withdrawal of consent, or the end of the study, whichever occurs first. Study participation is expected to average approximately 12 months per individual subject.

4.5. Overall Study Duration

The study begins when the first subject signs the informed consent. Subjects who are still receiving study treatment at the time of the primary analysis will be permitted to continue on study treatment until treatment withdrawal criteria are met (Section 5.5). All subjects will be followed for survival until death, withdrawal of consent, or the end of the study, whichever occurs first. The study will end and the final analysis will occur once 75% of subjects have achieved 2-year NRM, died or are lost to follow-up, whichever occurs first.

4.6. Study Termination

The investigator retains the right to terminate study participation at any time, according to the terms specified in the study contract. The investigator is to notify the institutional review board (IRB)/independent ethics committee (IEC) in writing of the study's completion or early termination, and send a copy of the notification to the sponsor or sponsor's designee and retain 1 copy for the site study regulatory file.

The sponsor may terminate the study electively or if required by regulatory decision. If the study is terminated prematurely, then the sponsor will notify the investigators, the IRBs and IECs, and the regulatory bodies of the decision and reason for termination of the study.

5. TREATMENT

5.1. Treatment Assignment

5.1.1. Subject Numbering and Treatment Assignment

Each subject will be identified in the study by a subject ID number, which is a combination of the site ID and subject number. Site staff should contact the interactive voice response system (IVRS) to obtain the subject ID number during screening.

Site staff will contact the IVRS to enroll the subject and obtain the initial study drug assignment. The investigator or designee will select the assigned bottles of study drug from their stock that correspond to the number provided by the IVRS, record the bottle numbers in the electronic case report form (eCRF), and dispense the study drug to the subject. All subsequent dispensing of study drug should follow this process. Full details will be provided in the IVRS manual.

All subject numbers will be 6 digits; the first 3 digits will be the site number, and the last 3 digits will be the subject's number. This subject number will be maintained throughout the study and will not be reassigned. Subjects who withdraw consent or discontinue from the study after being assigned a subject number will retain their initial number.

For subjects who signed an ICF but are not allocated and for subjects who are allocated but were not treated, refer to the eCRF Completion Guidelines for instruction on which eCRFs to complete.

5.1.2. Randomization

Not applicable.

5.2. Study Drugs

5.2.1. Ruxolitinib

5.2.1.1. Description and Administration

Ruxolitinib 5 mg tablets are round and white to off-white in color.

Subjects will begin treatment at ruxolitinib 5 mg BID; if hematologic parameters are stable and no treatment-related toxicity is observed after the first 3 days of treatment, the dose may be increased to 10 mg BID. Stable hematologic parameters are defined as the absence of $a \ge 50\%$ decrease in platelet counts and/or ANC relative to Day 1. Ruxolitinib may be taken without regard to food except on days when PK samples are drawn; on those days, subjects should be instructed to fast and refrain from taking ruxolitinib until PK samples are collected. See Section 7.7.1 for additional information.

Subjects may have dose reductions or modifications of ruxolitinib during the course of treatment based on AEs, clinical evaluation, and laboratory assessments. See Section 5.4.1 for dose modifications of ruxolitinib.

Subjects are permitted to remain on ruxolitinib treatment until withdrawal from study treatment is considered necessary as per Section 5.5.

